### **6.5 Study Team Training and Intervention Reliability**

All study team members have completed required human subjects training and have undergone protocol-specific training with respect to the intervention and all study procedures.

## **SECTION 7 STATISTICAL CONSIDERATIONS AND ANALYSIS**

Our primary outcome is the difference in change in glycemic variability in those randomized to LCSB restriction compared to controls, calculated as difference in average daily TIR in Weeks 11 and 12 compared to Weeks -1 and 0. Because no prior study has assessed glycemic variability before and after LCSB restriction, we have powered our study using changes before and after LCS consumption. Suez et al., reported a  $1564 \pm 1852$  (mg·dL·120 mins) $^{-1}$  increase in glucose AUC post-LCS versus baseline, in 7 volunteers consuming saccharin (equivalent to 4-5 diet sodas per day) for 1 week. Using a similar effect size, 13 subjects per group will provide 80% power to detect differences in glycemic control before and after LCS restriction versus control (G\*Power; V3). Because 60% (4 of 7) of participants were considered LCS-responders by Suez, we will randomize 20 participants to the intervention and control, respectively (n=40). 48 subjects (24 per group) will account for 20% attrition. However, because prior studies conducted by Drs. [name] and [name] in this patient population have generated 70-80% usable CGM data, we will conservatively enroll 60 subjects (n=30 per group). We will use 1:1 block randomization stratified by LCSB type (sucralose or aspartame + ace-K) to lay the groundwork for evaluating potential differences in effects of sucralose versus aspartame in future studies.

Univariate analyses will be performed using an intention to treat approach. The maximum number of days of glycemic data will be used without imputations for missingness. Bivariate associations will be examined using cross tabulations, odds ratios, and chi-squared tests; boxplots, mean differences, and ANOVA, and correlations, as appropriate. We will identify and validate outliers and non-parametric tests will be used in the case of non-normal data. By establishing strengths of crude associations and highlighting irregular data, descriptive analyses will be a reference for more complex models. Changes in glycemic variability and other metabolic outcomes pre/post intervention will be compared between the groups using ANOVA. Hypothesis

testing will be two-sided with a type I error of 0.05. Analyses will be summarized using regression estimates, p-values, and 95% CI and performed using SAS 9.4.

Study recruitment, enrollment, and rates of data completion will be used to examine feasibility. To assess acceptability, attrition rates will be examined, and qualitative interviews will be conducted using 8 open-ended questions to probe for participant acceptability, feasibility, and situations where adherence was most challenging. Adherence to beverage assignments will be operationalized as any consumption of LCSBs in violation of the study protocol. Data collected during qualitative interviews (for both interviews at end of full trial and for the separate interview on COVID-19 impacts on T1D management) will be transcribed and coded using standard methods and analyzed using content analysis. The codebook will include descriptive categories based on a priori research questions as well as data-driven categories to identify emergent themes. [name], and a trained RA will code the first 3 transcripts together to develop a preliminary codebook. The RA will independently code the remaining transcripts and modify the codebook as themes arise. The team will discuss any discrepancies in coding, after which [name] will make the final determination.

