### **2.3 Potential Risks**

It is possible that other participants and individuals external to the study may find out that a participant took part in the research, in which case, information derived may be conveyed to others external to the group.

**Blood Draws:** Although blood draws are a standard medical procedure, there is a risk of discomfort at the site of the needle entry or bruising at the site. There is also a remote risk of fainting or local infection associated with drawing blood. To address this, only skilled and well-trained phlebotomists will carry out these procedures.

**Continuous glucose monitoring (CGM):** The use of CGM for measurement of glycemic variability and 'time in range' may be challenging for some children and their parents. Although CGM is commonly used in children with T1D, some children may be fearful of the insertion or embarrassed to share their blood glucose levels. We will work with the child and parent to ensure the child is comfortable. We will also discontinue CGM if this becomes painful or problematic to the child or parent.

Dual energy X-ray absorptiometry (DXA): This instrument is used to measure body fat using low dose x-ray. This scan does give a small amount of radiation. Using the standard way of describing radiation exposure, subjects will receive an effective dose of less than one thousandth of one rem from each DXA scan. By comparison, the average person in the United States receives approximately this much radiation every day from natural background sources, such as the sun and from radioactive materials that are found naturally in the earth's air and soil.

Spot urine sample: We are not aware of any known risks from providing a spot urine sample. However, collecting the sample may be uncomfortable, burdensome, or embarrassing for some individuals. We have minimized this risk by having participants collect the urine sample in a private space and de-identifying the data collected to ensure that urine samples are not directly linked to the subject's identity.

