### **SECTION 3 Objectives and Endpoints**

#### **3.1 Primary Objective(s)**

To examine the effects of replacement of usual LCSB consumption with unsweetened still or seltzer water for 12 weeks on glycemic variability using continuous glucose monitoring (CGM) compared to control (continuation of usual LCSB consumption).

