#### **3.3 Primary Outcome Measure(s)**

Glycemic variability and HbA1c

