### **3.4 Secondary Outcome Measure(s)**

Visceral adiposity, lipid profiles, and systemic inflammation, impacts of COVID-19 pandemic on type 1 diabetes management from qualitative interviews

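### The primary outcome is two measures in Section 3.3 but one in Sections 3.1 and 7, and Section 7 labels a change in time in range as glycemic variability

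*Combined protocol and SAP*

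**What the plan says.** **How many primaries.** Section 3.3 lists "Glycemic variability and HbA1c". The primary objective in Section 3.1 concerns the effect "on glycemic variability using continuous glucose monitoring (CGM) compared to control" and does not mention HbA1c. Section 7 is in the singular: "Our primary outcome is the difference in change in glycemic variability". It never mentions HbA1c. The secondary outcomes in Section 3.4 are "Visceral adiposity, lipid profiles, and systemic inflammation, impacts of COVID-19 pandemic on type 1 diabetes management from qualitative interviews", so HbA1c has no place there either. Section 7 sets one error rate ("testing will be two-sided with a type I error of 0.05") with no split, order or success rule for two outcomes.

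**What the primary measures.** Section 7 names the outcome glycemic variability, but it is "calculated as difference in average daily TIR in Weeks 11 and 12 compared to Weeks -1 and 0". The Hypothesis (under Section 2.2) predicts more time in the target glycemic range. Section 2.3 mentions the two side by side: "The use of CGM for measurement of glycemic variability and 'time in range' may be challenging". No section defines a dispersion statistic such as SD or CV of glucose, and none gives the glucose limits for TIR. Table 1 (Section 6.4) labels HbA1c as glycemic control and lists glycemic variability separately.

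**The concern.** There are two separate faults.

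First, if TIR and HbA1c give different answers, the documents do not settle whether the trial met its primary outcome. If Section 3.3 governs, there are two primaries and no success rule. If Sections 3.1 and 7 govern, there is one, and HbA1c has no rank. The choice could then be made after the results are known.

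Second, the label and the calculation describe different quantities. TIR is the share of readings between two limits, so it depends on where the glucose distribution is centred as well as how wide it is. A TIR gain produced only by a lower mean would be reported, under Section 7's label, as an improvement in variability. No other planned measure would show that variability had not changed.

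**Working it through.** **The plan's own figures.** The plan gives no number for TIR, SD, CV or HbA1c, so there is none to reproduce on the label question. Its sample size uses a glucose-AUC change of 1564 with SD 1852, so d = 1564/1852 = 0.844. A two-sided paired t-test with this d has 79.8% power at n = 13, which is close to the stated 80% with 13 per group. I use d below only as an illustration. It is not a power estimate for TIR or HbA1c, and whether it suits the between-group contrast is a separate matter.

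**Step 1: does TIR change when spread does not?** Assumptions not in the documents: limits 70-180 mg/dL, and glucose either normal or lognormal.

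- Normal: TIR = Φ((180 − mean)/SD) − Φ((70 − mean)/SD).
- Lognormal: s² = ln(1 + (SD/mean)²), m = ln(mean) − s²/2, TIR = Φ((ln 180 − m)/s) − Φ((ln 70 − m)/s).

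Example (normal, SD 65): at mean 190, Φ(−0.154) − Φ(−1.846) = 40.64%; at mean 175, Φ(0.077) − Φ(−1.615) = 47.75%; gain 7.1 points.

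| SD (fixed) | TIR gain, mean 190 to 175, normal | TIR gain, lognormal | CV before and after |
|---|---|---|---|
| 60 | +8.2 | +10.4 | 31.6% to 34.3% |
| 65 | +7.1 | +9.4 | 34.2% to 37.1% |
| 70 | +6.2 | +8.4 | 36.8% to 40.0% |

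SD does not change and CV gets worse, but TIR improves under both shapes. Holding CV fixed instead leads to the same conclusion: with lognormal glucose and CV 36%, TIR is 78%, 68%, 56% and 45% at means of 140, 160, 180 and 200.

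**Step 2: does lower spread always raise TIR?** No. Take SD from 70 to 50 with the mean held:

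| Mean | TIR change, normal | TIR change, lognormal |
|---|---|---|
| 175 | +6.0 | +0.4 |
| 190 | +1.3 | −3.8 |
| 200 | −1.6 | −6.2 |
| 210 | −4.0 | −8.2 |

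The change is zero at a mean of about 194 (normal) or about 176 (lognormal). A real fall in spread can therefore lower TIR, but the mean at which this starts depends on the assumed shape.

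**Step 3: error rate with two primaries.** This applies only if Section 3.3 governs and success on either outcome is enough. Two tests at 0.05 give 1 − 0.95² = 9.75% under independence. For bivariate normal statistics, 1 − P(|Z₁| < 1.96, |Z₂| < 1.96) is 7.0% at an assumed correlation of 0.9. If both must succeed, or if only Section 7's outcome is tested, the rate does not exceed 0.05.

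**Step 4: what keeping two primaries would cost in power.** Two-sample noncentral t, d = 0.844, independent endpoints, at Section 7's 20, 24 and 30 per group. Let a be power at 0.025 and b power at 0.05. Per-endpoint Holm power = a + (b − a)·a; joint power when both must succeed = b².

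| Per group | a | b (single endpoint) | Holm, per endpoint | Both succeed |
|---|---|---|---|---|
| 20 | 63.3% | 74.0% | 70.1% | 54.7% |
| 24 | 72.7% | 81.7% | 79.2% | 66.7% |
| 30 | 83.1% | 89.5% | 88.5% | 80.2% |

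**The case against.** The best defence is that Section 7 already fixes the analysis. It gives the measure, the weeks and the between-group contrast, and these match the Hypothesis. HbA1c is measured at both visits and would be compared by ANOVA among the other metabolic outcomes, so only its rank is unclear. The study is a pilot seeking preliminary evidence. The sentence in Section 2.3 that sets variability beside time in range is a risk paragraph about wearing a sensor, and is weak evidence that the protocol meant to define two constructs.

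Much of this stands. The planned TIR calculation can be identified, and the Section 2.3 wording carries little weight. But nothing gives Section 7 precedence over the section headed Primary Outcome Measure(s), and if it had precedence, HbA1c would still be unranked and the label would still not match. The pilot status lowers the stakes without removing the inconsistency, because Section 7 names a primary outcome with 80% power and a 0.05 test.

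A reader might infer three stronger things that the documents do not support:

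- **That the trial runs at a 9.75% false-positive rate.** No section says that success on either outcome would suffice, and Section 7 names a single primary.
- **That there is a fixed mean glucose above which less spread lowers TIR.** The documents give no glucose distribution, and the break-even moves from about 194 to about 176 with the assumed shape.
- **That a Holm procedure would cost the full drop to power at 0.025.** That is the Bonferroni cost. Holm tests the second endpoint at 0.05 once the first succeeds, so the illustrated per-endpoint loss is about 1 to 4 points.

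**Conclusion.** The point holds, with moderate severity. Section 3.3 conflicts with Sections 3.1 and 7 on the number of primary outcomes, HbA1c is unranked if the latter govern, and the measure called glycemic variability is TIR. These findings rest on the text alone.

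The size of the label problem rests on assumed limits of 70-180 mg/dL and an assumed glucose shape. A mean shift of 15 mg/dL with SD unchanged moves TIR by roughly 6 to 10 points under either shape. The direction of that result does not depend on which shape is chosen; the effect of reduced spread on TIR does. Inflation of the error rate is conditional and is not the basis for the severity. The missing TIR limits are a lesser gap, which the same edit closes.

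**What to change.** Before outcome data are analysed, state one primary outcome in the same words in Sections 3.1, 3.3 and 7.

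**Default**, following Section 7's calculation and the Hypothesis:

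- Primary: between-group difference in change in average daily TIR, Weeks 11-12 against Weeks -1 and 0, tested two-sided at 0.05, called TIR, with its lower and upper glucose limits stated.
- Move HbA1c to Section 3.4.
- Add within-person SD or CV from the same CGM download as a secondary outcome, so that any statement about variability rests on a measure of variability.
- Align the labels in the Protocol Summary (outcome measures and statistical analysis) and Table 1, and the purpose statement under Study Interventions in Section 2.2.

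Cost: wording changes and one extra summary from data already collected. No new visits or samples are needed, and this point does not change the sample size. HbA1c loses primary status.

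**Alternatives for the sponsor:**

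- (A) If variability itself is the intended primary, calculate it as SD or CV and make TIR secondary. This needs no new data, and the borrowed glucose-AUC effect is no closer to TIR than to SD or CV.
- (B) If HbA1c stays as a second primary, state whether either or both must succeed. If either suffices, use Holm. If both must succeed, no alpha adjustment is needed, but the lower joint power should be stated. Step 4 illustrates both costs.

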
Outcome Measures:
	
HbA1c, CRP, IL-6, TNF-<math>\alpha</math>, LDL, HDL, triglycerides, and free fatty acids (FFA) measured in blood samples. Sucralose and ace-K concentrations in biological fluids, including urine. Visceral fat area from DXA or BodPod. Continuous blood glucose to assess glycemic variability, photo-assisted food records to assess adherence to LCSB restriction and any changes in diet throughout study, beverage log to assess adherence, satisfaction survey, Diabetes Self-Care Inventory (SCI), physical activity questionnaire (PROMIS), COVID-19 diabetes management questionnaire, Eating Attitudes (EAT) questionnaire, and an in-depth interview. Additional, in-depth interview about COVID-19 impacts on T1D management (for those who screen ineligible for full study and those who participate in DRINK and are interested in also participating in this additional interview)

Study Intervention/ Procedures:
	
Children will be randomly assigned to either replace their LCSB consumption with still or seltzer water or to continue their usual LCSB consumption for 12 weeks. Parents who participate in the COVID-19 interviews will undergo a brief qualitative interview with a trained interviewer.

Statistical Analysis:
	
Univariate analyses and one-way ANOVA will be used to assess group differences in glycemic variability and other metabolic outcomes pre/post intervention. Bivariate associations will be examined using odds ratios, chi-squared, boxplots, mean differences, and ANOVA, as appropriate. Qualitative data collected during interviews will be transcribed verbatim and thematically coded.

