## **6.4 Description of Study Procedures/Evaluations**

We propose a two-arm randomized controlled trial (RCT) during which 60 children with T1D will either replace usual LCSB consumption with unsweetened still or seltzer water (LCSB restriction) or continue usual LCSB use (control) for 12 weeks. This will provide ample time to evaluate intervention feasibility and acceptability, while enabling us to generate preliminary evidence of whether LCSB restriction may improve cardiometabolic health.

Eligible participants will be scheduled for a baseline visit in the Clinical Research Unit (CRU) at CNMC. During the week prior, they will be instructed to continue usual dietary habits and complete an online photo-assisted 7-day food record, with parental assistance. While we recognize that parents are unlikely to accurately report all of their child's intake because they are not always with them (e.g., during school), dietary data for children under 14 years are most accurately reported when provided by the parent or child and parent combined.

The baseline visit will take place in the CRU, where height and weight will be measured, a spot urine sample will be collected, and a blood draw will be performed. Participants will have the DEXCOM G6™ sensor removed and their CGM data downloaded. In a subset of participants (n=30) a DXA scan or BodPod will also be performed, as R21 budget constraints preclude DXA or BodPod on all 60 subjects. Subjects will be

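### The 80% power claimed for 13 per group does not fit the planned between-group test: on the plan's own effect size it is about 54%, and 80% needs 24 evaluable per group

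*Combined protocol and SAP*

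**What the plan says.** All the inputs are in Section 7. The estimand is a between-group one: "Our primary outcome is the difference in change in glycemic variability in those randomized to LCSB restriction compared to controls", measured as average daily time in range in Weeks 11 and 12 against Weeks -1 and 0. The test is given there as "Changes in glycemic variability and other metabolic outcomes pre/post intervention will be compared between the groups using ANOVA", and the Protocol Summary agrees: "one-way ANOVA will be used to assess group differences in glycemic variability and other metabolic outcomes pre/post intervention". Tests are two-sided at 0.05 and allocation is 1:1.

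The planning effect is borrowed from a published saccharin study: an increase in glucose AUC of 1564 ± 1852 from baseline in 7 volunteers. From a similar effect size the plan concludes that "13 subjects per group will provide 80% power to detect differences in glycemic control before and after LCS restriction versus control", citing G*Power without naming the test. It then raises 13 to 20 per group because about 60% (4 of 7) of those volunteers were responders. Next, "48 subjects (24 per group) will account for 20% attrition". Finally it goes to 30 per group because earlier work in this population yielded 70-80% usable CGM data.

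Section 6.4 describes the aim as "enabling us to generate preliminary evidence of whether LCSB restriction may improve cardiometabolic health".

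**The concern.** The effect size describes change within one group, but the power statement is about one group's change against another's. A between-group contrast carries the sampling error of two means, so at the same standardised effect it needs roughly twice as many subjects in each group as a one-group test needs in total. A requirement of 13 per group at an effect near 0.84 looks like the one-group answer.

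Every later step (20, 24, 30 per group) multiplies up from the 13. If the base is too small, the margin presented as cover for non-responders, dropout and lost CGM data is partly or wholly used up in reaching the correct base. A reader who takes the 80% at face value would read a null primary result as stronger evidence of no effect than it is.

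**Working it through.** **Inputs (all Section 7).** Mean change 1564; spread 1852, read as the SD of within-person change; two-sided α = 0.05; 1:1 allocation; 20% attrition; 70-80% usable CGM data. Two further assumptions are needed: zero mean change in controls, and equal SDs in the two groups.

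**Effect size.** d = 1564 / 1852 = 0.8445.

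**Reproducing the 13.** One-group paired t-test: df = n − 1, noncentrality d√n. At n = 13 the noncentrality is 0.8445 × √13 = 3.045 and the critical value is 2.179, so power is 79.8% (n = 14 gives 83.1%). The plan's figure is therefore recovered as a one-group calculation. Since the plan names no test, this origin is likely but unconfirmed, and the conclusion does not depend on it.

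**The planned test.** A two-group ANOVA on change is a two-sample t-test: df = 2n − 2, noncentrality d√(n/2).

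- n = 13: 0.8445 × √6.5 = 2.153, critical value 2.064, power 54.2%.
- n = 24: 0.8445 × √12 = 2.925, critical value 2.013, power 81.7%.

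| Evaluable per group | Power at d = 0.844 | d detectable with 80% power |
|---|---|---|
| 13 | 54.2% | 1.15 |
| 17 | 66.6% | 0.99 |
| 19 | 71.7% | 0.93 |
| 20 | 74.0% | 0.91 |
| 21 | 76.1% | 0.89 |
| 23 | 79.98% | – |
| 24 | 81.7% | 0.83 |
| 30 | 89.5% | – |

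The requirement is 24 per group. Even a one-sided 0.05 test at 13 per group gives only 67.3%.

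**What 30 enrolled per group delivers.** The plan does not say how the two losses combine.

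- In sequence, as the steps 20, 24, 30 suggest: 30 × 0.8 × 0.7 = 16.8 to 30 × 0.8 × 0.8 = 19.2, so about 17-19 evaluable and 67-72% power (66% at the unrounded 16.8).
- If the usable-CGM rate already includes dropouts: 30 × 0.7 = 21 to 30 × 0.8 = 24, so 76-82% power.
- With no losses: 30, so 90% power.

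**The case against.** **The spread is not labelled, so the SD-of-change reading is a choice.** This is true. If 1852 were the SD at a single time point, the standardised change would be d / √(2(1 − r)), where r is the pre/post correlation. Power at 13 per group would then be 54% at r = 0.5, 64% at 0.6, 76% at 0.7, and 80% only at about 0.73. The documents give no correlation, and the ± is attached to the increase itself, so SD of change is the natural reading. If it were a standard error, d would be 0.8445 / √7 = 0.32, with 17% power at 20 per group and 23% at 30. The SD reading should be stated as an assumption.

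**A G*Power repeated-measures interaction can return 13 per group.** With f = d/2 and correlation 0, a total of 24 gives 79.8% and a total of 26 gives 83.2%. But its noncentrality is d²N/2 = 9.27 at N = 26, against d²N/4 = 4.64 for the planned comparison when 1852 is the SD of change. The agreement comes from doubling the noncentrality.

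**The responder step compensates.** It does not. As Section 7 reports it, the effect covers all 7 volunteers, so non-responders are already averaged in, and 20 per group still gives only 74%.

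**Nobody will analyse 13 per group, and 60 may be enough.** In part this stands. At best 24 per group remain, and the 80% target is met. That also holds if the usable-CGM rate is a share of data rather than of children, so that only attrition removes children (30 × 0.8 = 24). At the other end power is about 67%.

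**It is a pilot, and an effect from 7 people is very imprecise.** Both points are fair. On the same reading, the 95% interval for d is about −0.06 to 1.70 (t = 0.8445 × √7 = 2.234 on 6 df). That is a good reason to report detectable effects alongside power. It does not justify keeping a formal 80% claim that is arithmetically wrong.

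**Conclusion.** The claim of 80% power at 13 per group is wrong as written for the comparison it names. Power there is 54%, reaching 80% needs 24 evaluable per group, and 13 per group would suffice only for d of about 1.15, some 36% above the plan's own effect (1.145 / 0.8445 = 1.36). At the enrolled 60 the realistic power is 67-82%, so the shortfall runs from none to about 13 percentage points. This rests on 1852 being the SD of within-person change, zero mean change in controls, equal SDs, and a saccharin effect on glucose AUC carrying over to time in range. Power below 80% is defensible for a pilot; the power statement in Section 7 is what needs correcting.

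**What to change.** In Section 7, replace the sentences from the one claiming 13 per group through the one setting enrolment at 60 with text along these lines:

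> For the between-group comparison of change, d = 0.84 requires 24 evaluable children per group for 80% power (two-sided 0.05). Enrolment will be 60 (30 per group). About 17-24 evaluable per group are expected, depending on whether attrition (20%) and unusable CGM data (20-30%) overlap. This gives about 67-82% power, or 80% power for d = 0.99 to 0.83. The calculation assumes that ±1852 is the SD of within-person change, that mean change in controls is zero, that SDs are equal, and that an effect on glucose AUC after saccharin carries over to time in range.

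This drops the responder inflation, which counts non-responders a second time. A clause noting that the effect comes from only 7 people would be a useful addition.

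The cost is one reworded paragraph and a less favourable power figure. No further children are enrolled, and design and analysis are unchanged.

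### The step from 13 to 20 per group cannot be derived from the responder share given for it, and a responder inflation does not fit the planned intention-to-treat comparison

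*Combined protocol and SAP*

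**What the plan says.** All of this is in Section 7 (Statistical Considerations and Analysis) of the combined protocol and SAP.

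- **Planning effect.** A mean change of 1564 with SD 1852 is taken from a cited study, described as an "increase in glucose AUC post-LCS versus baseline, in 7 volunteers consuming saccharin" for one week. No restriction to responders is stated.
- **Starting size.** With a similar effect size, "13 subjects per group will provide 80% power to detect differences in glycemic control".
- **Responder step.** "Because 60% (4 of 7) of participants were considered LCS-responders" in that study, the plan continues, "we will randomize 20 participants to the intervention and control, respectively (n=40" in total). This is the only reason given for moving from 13 to 20, and no formula is shown.
- **Later steps.** The 20 becomes 24 per group for 20% attrition, and then 30 per group because earlier studies gave 70-80% usable CGM data.
- **Analysis.** "Univariate analyses will be performed using an intention to treat approach". The group comparison is given as follows: "Changes in glycemic variability and other metabolic outcomes pre/post intervention will be compared between the groups using ANOVA". Tests are at the 5% level, two-sided. Allocation is by "1:1 block randomization stratified by LCSB type".

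The section defines no responder for this trial and plans no responder subset or enrichment.

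**The concern.** A reader who tries to retrace the sample size stops at this step, since 20 does not come out of 13 and 60% by the obvious calculation. More important is what a responder adjustment is for. Dividing by a responder share makes sense when non-responders will be removed and a fixed number of responders must remain. An intention-to-treat comparison keeps everyone. The question there is whether the planning effect is already an average over everyone or has to be averaged down, and the section does not address it.

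The figures of 24 and 30 per group are built on the 20. The text also leaves the impression that non-response has been properly allowed for. Depending on what was meant, it has been counted twice or allowed for by the wrong rule.

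**Working it through.** **Inputs (Section 7).** Mean 1564, SD 1852, reported in 7 volunteers; 13 per group for 80% power; responder share p = 0.60 as printed, or 4/7 = 0.571 exactly; 20 per group after the step; 20% attrition; 70-80% usable CGM data; 30 per group enrolled; two-sided alpha 0.05.

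**1. The starting 13.** d = 1564/1852 = 0.844. A one-sample (paired) t-test needs n = 13.06 for 80% power and has 79.8% power at 13, so 13 is reproduced to rounding. The section does not name the test behind the figure. A repeated-measures interaction with f = d/2 and zero correlation also gives 13 per group.

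**2. From 13 to 20 by division.**

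| Share used | 13/p | Rounded up | Expected responders in 20 |
|---|---|---|---|
| 0.60 | 21.67 | 22 | 20 × 0.60 = 12.0 |
| 4/7 | 22.75 | 23 | 20 × 4/7 = 11.4 |

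To get 20 by division the share would have to be 13/20 = 65%. Another simple form, 13 × (2 − p), gives 18.2 or 18.6.

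**3. Does the type of correction fit the analysis?** There are two readings.

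*(a) The effect is the mean over all 7 volunteers, as the section reads.* Responders and non-responders are both in the mean and the SD. The intention-to-treat contrast targets that same kind of average, so the inflation factor is 1 and the plan's own figure stays at 13.

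*(b) The effect applies to responders only (not stated).* Assume also that non-responders have zero effect and that the SD is unchanged. The average effect is then p × d, and n grows by about 1/p²: 1/0.36 = 2.78, or 49/16 = 3.06. Keeping the one-sample calculation of step 1:

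- p = 0.60: 0.844 × 0.60 = 0.507, n = 32.5, so 33
- p = 4/7: 0.844 × 4/7 = 0.483, n = 35.7, so 36

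Neither reading gives 20.

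**4. What the fixed enrolment gives.** This uses the undiluted d = 0.844 in a two-sample t-test, which matches the planned between-group comparison of changes.

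| Evaluable per group | Power |
|---|---|
| 30 | 90% |
| 24 | 82% |
| 20 | 74% |
| 19 | 72% |
| 17 | 67% |

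The last two rows apply if attrition and unusable CGM data act one after the other: 30 × 0.80 × 0.80 = 19.2 and 30 × 0.80 × 0.70 = 16.8.

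**The case against.** The best defence has four parts.

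- **The arithmetic gap is small.** It is 2 to 3 children per group, and writing 57% as 60% is ordinary rounding. This stands, and the gap alone would be a minor correction. Division is also an imputed rule, since the plan states none; what can be said is that the step is unexplained and does not match it.
- **On the natural reading, 20 exceeds the plan's own 13.** The step then errs on the large side. This also stands.
- **The 1/p² rule needs assumptions.** It requires no effect in non-responders and an unchanged SD, and a mixture of the two kinds of participant would itself alter the SD. So 33-36 is a conditional figure, not a finding about this trial.
- **The consequence is limited.** Enrolment is 30 per group, in a study that the Protocol Summary calls a pilot and that Section 6.4 says is to generate preliminary evidence.

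A reader might go further and infer that the trial is badly underpowered because non-response was allowed for far too little. The documents do not support that. Nothing in them says that the borrowed effect belongs to responders only, and the description of 7 volunteers points the other way. Adding the change from a one-sample to a two-sample calculation would enlarge the shortfall further, but that is a separate question from the responder step.

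None of this supplies a derivation of 20, or a reason for a responder inflation under intention to treat.

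**Conclusion.** The concern holds in a limited form. The move from 13 to 20 per group cannot be derived from the reason given: division yields 22 or 23, and 20 per group would contain 11 to 12 expected responders, fewer than 13. The correction is also of the wrong kind for an intention-to-treat comparison. On the section's own description no inflation is due; only under an unstated responders-only reading, with the two further assumptions above, would the one-sample calculation rise to 33-36 per group. The direction of the error is therefore open, and it is not shown that 20 is too small.

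What matters in practice is the power of the planned test. It is about 90% with 30 evaluable per group, 74% with 20, and 67-72% with 17 to 19. These figures assume that d = 0.844, a glucose AUC change after saccharin, carries over to the between-group difference in change in time in range. The lowest range also assumes that attrition and unusable CGM data compound.

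**What to change.** In Section 7:

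1. Delete the sentence that raises 13 to 20 on account of the responder share.
2. State that the planning effect is the average over responders and non-responders, which is what the intention-to-treat contrast estimates.
3. Restate the sample-size paragraph from the fixed enrolment of 60. Say how many per group are expected to be evaluable, whether attrition and unusable CGM data are taken to compound, and what power the between-group comparison of changes then has.

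If the sponsor did mean a responders-only effect, the plan should say so, show the effect multiplied by the responder share, list the assumptions about non-responders and the SD, and give the resulting power for 60 enrolled.

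The change is to protocol and SAP wording only, with no change in enrolment or procedures. The downside is that the stated power is likely to look less favourable than the present text suggests.
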